7.1. Discontinuation of Study Intervention

Study intervention may be temporarily withheld or permanently discontinued during the study.

Participants who permanently discontinue study intervention early will undergo early termination procedures, which include:

- an ETV, and
- PTFU visits (V801 and V802).

The investigator will complete any AE reporting and follow-up (Section 8.3).

7.1.1. Permanent Discontinuation from Study Intervention

In rare instances, it may be necessary for a participant to permanently discontinue (definitive discontinuation) study intervention. If study intervention is definitively discontinued, the participant will remain in the study to have ETV and PTFU visits. See the SoA (Section 1.3) for data to be collected at the time of discontinuation of study intervention and follow-up and for any further evaluations that need to be completed.

Possible reasons leading to permanent discontinuation of study intervention:

- Participant decision:
 - the participant or the participant's designee, e.g., parents or legal guardian, requests to discontinue the study intervention.

Participants will be discontinued from the study intervention under the following circumstances:

- Neutrophil (segmented) counts:
 - $<500 \text{ cells}/\mu\text{L}$
 - $\geq 500 \text{ and } < 1000 \text{ cells}/\mu\text{L}$ (based on 2 test results; the second test performed within 1 week from knowledge of the initial result)
 - $\geq 1000 \text{ and } < 1500 \text{ cells}/\mu\text{L}$ (based on 3 test results) and an infection that is not fully resolved
 - WBC count $< 1000 \text{ cells}/\mu\text{L}$ ($1.00 \times 10^3/\mu\text{L}$ or 1.00 billion/L)
 - absolute neutrophil count (ANC) $< 500 \text{ cells}/\mu\text{L}$ ($0.50 \times 10^3/\mu\text{L}$ or 0.50 billion/L)
 - lymphocyte count $< 200 \text{ cells}/\mu\text{L}$ ($0.20 \times 10^3/\mu\text{L}$ or 0.20 billion/L)
 - hemoglobin $< 6.5 \text{ g/dL}$ ($< 65.0 \text{ g/L}$)
 - platelet count $< 50,000 \text{ cells}/\mu\text{L}$.

Note: Temporary interruption rules (see Section 7.1.3) must be followed, where applicable. For laboratory values that meet permanent discontinuation thresholds, the study intervention should be discontinued. However, if in the opinion of the investigator the laboratory abnormality is due to intercurrent illness such as cholelithiasis or another identified factor, laboratory tests may be repeated. Only when the laboratory value meets resumption thresholds following the resolution of the intercurrent illness or other identified factor may the investigator restart the study intervention after consultation with the Sponsor-designated medical monitor.

In addition, participants will be discontinued from the study intervention in the following circumstances:

- The participant experiences a severe AE or SAE or has a clinically significant change in a laboratory value that, in the opinion of the investigator, merits discontinuation of the study intervention and appropriate measures being taken. This includes evidence of active viral hepatitis or active tuberculosis (TB). In such cases, the Sponsor or its designee is to be notified immediately.
- Clinically significant systemic hypersensitivity reaction following SC administration of study intervention that does not respond to symptomatic medication or results in clinical sequelae
- The participant becomes pregnant
- The participant develops a malignancy (Note: participants may be allowed to continue if they develop no more than 2 non-melanoma skin cancers during the study)
- The participant has a positive TB test using QuantiFERON®-TB Gold or T-Spot or purified protein derivative (PPD) and is assessed as having latent TB infection (see Section 8.2.7), and/or develops symptoms or signs of tuberculosis.
- if the participant develops active suicidal ideation with some intent to act with or without a specific plan,

-OR-

if the participant develops suicide-related behaviors,

- then it is recommended that the participant be assessed by a psychiatrist or appropriately trained professional to assist in deciding whether the participant is to be discontinued from the study.

Participants discontinuing from the study intervention prematurely for any reason should complete AE and other follow-up procedures per the SoA (Section 1.3), Safety Assessments (Section 8.2), and Adverse Events and Serious Adverse Events (Section 8.3) of this protocol .

7.1.2. Liver Chemistry Stopping Criteria

The study intervention should be interrupted or discontinued if one or more of these conditions occur:

Elevation	Exception
ALT or AST $>5 \times$ ULN	
ALT or AST $>3 \times$ ULN and either TBL $>2 \times$ ULN or INR >1.5	In participants with Gilbert's syndrome, doubling of direct bilirubin should be used for drug interruption/ discontinuation decisions rather than TBL $>2 \times$ ULN.
ALT or AST $>3 \times$ ULN with the appearance of fatigue, nausea, vomiting, right upper quadrant pain or tenderness, fever, rash, and/or eosinophilia ($>5\%$)	
ALP $>3 \times$ ULN, when the source of increased ALP is the liver	
ALP $>2.5 \times$ ULN and TBL $> 2 \times$ ULN	In participants with Gilbert's syndrome, doubling of direct bilirubin should be used for drug interruption/ discontinuation decisions rather than TBL $>2 \times$ ULN.
ALP $>2.5 \times$ ULN with the appearance of fatigue, nausea, vomiting, right upper quadrant pain or tenderness, fever, rash, and/or eosinophilia ($>5\%$)	

Abbreviations: ALP = alkaline phosphatase; ALT = alanine aminotransferase; AST = aspartate aminotransferase; FDA = Food and Drug Administration; INR = international normalized ratio; TBL = total bilirubin level; ULN = upper limit of normal.

Source: FDA 2009.

Resumption of the study intervention can be considered only in consultation with the Lilly-designated medical monitor and only if the liver test results return to baseline and if a self-limited non-drug etiology is identified.

7.1.3. Temporary Discontinuation

In some circumstances, participants may need to temporarily interrupt treatment as a result of AEs or abnormal laboratory values that may have an unclear relationship to the study intervention. See Section 8.2.7 for details regarding managing participants who test positive for TB at any time during the study.

The abnormal laboratory values as reason for temporary discontinuation of study intervention may include HBV DNA results that are reported as positive, or as detecting HBV DNA, but HBV DNA is below the level of quantification. The Sponsor's designated medical monitor should be contacted regarding study status of the participant. HBV DNA testing is to be repeated as soon as is feasible. If HBV DNA is confirmed as positive, the participant must be permanently discontinued from study intervention (Section 7.1.1).

Participants requiring surgery at any time during the study should interrupt administration of the study intervention beginning 8 weeks before the surgery, or as early as possible, and resume administration of the study intervention only after complete wound healing.

7.2. Participant Discontinuation/Withdrawal from the Study

A participant may withdraw from the study:

- at any time at the participant's own request;
- at the request of the participant's designee (e.g., parents or legal guardian);
- at the discretion of the investigator for safety, behavioral, compliance, or administrative reasons;
- if enrolled in any other clinical study involving an investigational product, or enrolled in any other type of medical research judged not to be scientifically or medically compatible with this study;
- if participation in the study needs to be stopped for medical, safety, regulatory, or other reasons consistent with applicable laws, regulations, and good clinical practice (GCP) or
- if the participant, for any reason, requires treatment with a therapeutic agent that is prohibited by the protocol and has been demonstrated to be effective for treatment of the study indication. In this case, discontinuation from the study occurs prior to introduction of the new agent.

Discontinuation is expected to be uncommon.

At the time of discontinuing from the study, if possible, an ETV should be conducted, as shown in the SoA (Section 1.3). See the SoA for data to be collected at the time of study discontinuation and follow-up and for any further evaluations that need to be completed. The participant will be permanently discontinued both from the study intervention and from the study at that time.

If the participant withdraws consent for disclosure of future information, the Sponsor may retain and continue to use any data collected before such a withdrawal of consent. If a participant withdraws from the study, the participant may request destruction of any samples taken and not tested, and the investigator must document this in the site study records.

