4.1.4. Post-Treatment Follow-Up Period (Period 4)

All participants receiving at least 1 dose of study intervention will enter the Post-Treatment Follow-Up Period (Period 4) for a minimum of 4 weeks, beginning after their last regularly scheduled visit at Week 24 (or the date of their ETV).

Required study visits should occur at 4 weeks (Visit 801) after the last regularly scheduled visit at Week 24 (or the date of the participant's ETV), except for participants with a concurrent infection that requires systemic anti-infective therapy (described below).

If, at Visit 801, a participant's neutrophil count is ≥ 1500 cells/ μ L or greater than or equal to the participant's baseline neutrophil count, the participant's participation in the study will be considered complete unless the investigator determines additional follow-up may be necessary. An additional study visit (Visit 802) 8 weeks after Visit 801 may be required for appropriate participant management (described below).

If, at the last scheduled visit or ETV, a participant's neutrophil count is < 1500 cells/ μ L ($< 1.50 \times 10^3/\mu$ L or < 1.50 GI/L) and less than the participant's baseline neutrophil count, the following measures should be taken:

- Participants with concurrent infection: If there is a concurrent infection that requires systemic anti-infective therapy, the participant should receive appropriate medical care and a repeat test for neutrophil count should be performed at least Q4W (or sooner as appropriate) until resolution of infection. Upon resolution of infection, the neutrophil count should be monitored using the required study visits in the Post-Treatment Follow-Up Period (Period 4) design at Visits 801 (4 weeks after resolution of infection) and 802 (8 weeks after Visit 801); additional visits may be required depending on the degree of neutropenia.
- Participants without concurrent infection: If there is no concurrent infection that requires systemic anti-infective therapy, the neutrophil count should be monitored using the required study visits in the Post-Treatment Follow-Up Period (Period 4) design, Visits 801 (4 weeks post- ETV or last regularly scheduled visit at Week 24) and 802 (if necessary); additional visits may be required depending on the degree of neutropenia.
- For Visit 801 and subsequent visits, the following monitoring applies:

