 - As long as a participant's neutrophil count is < 1000 cells/ μ L ($< 1.00 \times 10^3/\mu$ L or < 1.00 GI/L) at any follow-up visit, the participant should return for additional visits at least Q4W (unscheduled visits may be required).
 - As long as a participant's neutrophil count is ≥ 1000 cells/ μ L and < 1500 cells/ μ L ($\geq 1.00 \times 10^3/\mu$ L and $< 1.50 \times 10^3/\mu$ L or ≥ 1.00 GI/L and < 1.50 GI/L) at any follow-up visit, the participant should return for additional visit(s) at least every 4 to 8 weeks (unscheduled visits may be required).

- If at Visit 802 the participant's neutrophil count remains <1500 cells/ μ L ($<1.50 \times 10^3/\mu$ L or <1.50 GI/L) and less than the participant's baseline neutrophil count or if the investigator deems additional follow-up may be necessary, the investigator in consultation with Eli Lilly and Company (Lilly) or qualified designee will determine the appropriate management of the participant and the appropriate timing of additional contact(s) or visit(s).
- If at Visit 802 the participant's neutrophil count is ≥1500 cells/ μ L ($\geq1.50 \times 10^3/\mu$ L or ≥1.50 GI/L) or greater than or equal to the participant's baseline neutrophil count (whichever is lower), the participant's participation in the study will be considered complete unless the investigator deems additional follow-up necessary.

For participants who have entered Period 4, PsO and PsA therapy is allowed, as determined appropriate by the investigator.

Note: Eli Lilly and company will provide study medication only until Week 20. Eli Lilly and company will not provide the post-trial/compassionate use for study intervention as it will be commercially available in India.

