- Any post-study pregnancy-related SAE considered reasonably related to the study intervention by the investigator will be reported to the Sponsor as described in protocol Section 8.3.1. While the investigator is not obligated to actively seek this information in former study participants, he/she may learn of an SAE through spontaneous reporting.
- Any female participant who becomes pregnant while participating in the study will discontinue study intervention. If the participant is discontinued from the study, follow the standard discontinuation process and continue directly to the follow-up phase. The follow-up on the pregnancy outcome should continue independent of intervention or study discontinuation.

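### Protocol Section 7.2, read literally, ends study participation at the early termination visit even for dosed, still-consenting participants whom Sections 4.1 and 4.1.4 send into post-treatment follow-up (minor)

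*Protocol*

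**What the plan says.** Section 7.2 lists the ways a participant may leave the study. Besides requests by the participant or a designee, the list includes exit "at the discretion of the investigator for safety, behavioral, compliance, or administrative reasons", and exit because a prohibited therapy effective for the study indication is needed. For the latter it adds: "In this case, discontinuation from the study occurs prior to introduction of the new agent".

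The next paragraph asks for an ETV if possible and then says: "See the SoA for data to be collected at the time of study discontinuation and follow-up". It closes with: "The participant will be permanently discontinued both from the study intervention and from the study at that time". A separate paragraph on withdrawn consent and stored samples follows, but nothing in it limits the closing sentence to those who withdraw consent.

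Section 4.1.4 states: "All participants receiving at least 1 dose of study intervention will enter the Post-Treatment Follow-Up Period (Period 4) for a minimum of 4 weeks". That period runs from the Week 24 visit or the ETV, and no exception is made for exits under 7.2. Section 4.1 adds that all participants should be monitored through Period 4. Section 4.1.4 also says: "For participants who have entered Period 4, PsO and PsA therapy is allowed, as determined appropriate by the investigator".

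The Schedule of Activities places Visit 801 four weeks after the last visit, with a window of 4 days either way, and marks only Visit 802 as needed on indication. Section 8.3.1 collects AEs until participation ends. Section 9.5.5.1 plans a summary of follow-up emergent AEs, meaning those that start or worsen after the Week 24 visit or the ETV.

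**The concern.** A participant cannot both leave the study at the ETV and enter a follow-up period of at least 4 weeks that starts at the ETV. For someone who withdraws consent, leaving at once is proper. For someone removed by the investigator, possibly for a safety reason, or moved to another therapy, consent to follow-up may still stand, and these are people whose post-treatment course is of interest in a study whose primary objective is safety.

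At stake are the AEs that first appear after the ETV and the Visit 801 neutrophil count. Section 4.1.4 relies on Period 4 for the latter: when the count at the last visit is low and below baseline and there is no infection needing systemic treatment, "the neutrophil count should be monitored using the required study visits in the Post-Treatment Follow-Up Period (Period 4) design". With two rules in the protocol, sites may act differently, and the follow-up emergent AE summary would then be incomplete in a way that cannot be read from the tables.

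**Working it through.** The protocol states no figure on this point, so the check is a comparison of texts followed by simple date arithmetic.

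**1. Scope of the sentence.** It follows the whole list of exits and has no qualifier. It therefore covers investigator discretion and need of a prohibited therapy as well as withdrawal of consent.

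**2. Texts side by side.**
- Ends participation at the ETV: the closing sentence of the ETV paragraph in 7.2.
- Sends dosed participants into follow-up: 4.1.4 (all with at least 1 dose) and 4.1 (all monitored through Period 4).
- Does not fit an exit at the ETV: the sentence in 7.2 just before the closing one, which points to the Schedule of Activities for follow-up; Section 7.1, which gives the ETV plus Visits 801 and 802 to those who permanently stop study intervention early; and Section 8.3.2 on pregnancy: "If the participant is discontinued from the study, follow the standard discontinuation process and continue directly to the follow-up phase".

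One sentence stands against the rest, so the 7.2 sentence is the one out of line.

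**3. Consequence of a literal reading.** If participation ends at the ETV, AE collection ends there too (8.3.1), and Visit 801 has no basis.

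**4. Size per affected participant.** Visit 801 = last visit + 28 ± 4 days, so 28 − 4 = 24 to 28 + 4 = 32 days of AE collection after the ETV, against 0 under the literal wording.

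**5. Observation after the last dose.**
- Completer: last dose at Week 20, day 140. Visit 6 at day 168 ± 5 is 23 to 33 days later. Adding Visit 801 gives 23 + 24 = 47 to 33 + 32 = 65 days; nominally 28 + 28 = 56.
- Exit under the literal 7.2, assuming that the ETV comes before the next dose is due (the protocol does not fix this timing): 0 to 14 days while dosing is every 2 weeks, 0 to 28 days while it is every 4 weeks.
- The same exits with Visit 801: 0 + 24 = 24 to 14 + 32 = 46 days, and 0 + 24 = 24 to 28 + 32 = 60 days.

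**6. Number affected.** Section 9.7 plans 250 participants with about 10% discontinuing: 250 × 0.10 = 25, and 250 − 25 = 225, which agrees with the protocol's own figure. The share leaving by the two routes is not given. Against the planning figure the number lies anywhere from 0 to about 25, and actual discontinuations may exceed the plan.

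**The case against.** The best reply is that the protocol already tells sites what to do. Section 7.2 itself points to follow-up one sentence earlier. The closing sentence also stops study intervention, so every exit during treatment falls under the rules for stopping intervention as well: 4.1.2 and 4.1.3 (ETV, then Period 4, whatever the reason), 7.1 (ETV plus Visits 801 and 802) and 7.1.1 (AE and other follow-up procedures per the Schedule of Activities). Section 8.3.2 shows that a participant discontinued from the study can still go on to follow-up. This stands, and it settles what is intended. It does not cancel an explicit statement that participation ends, on which the AE collection window in 8.3.1 depends.

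It is also fair to say that most safety data are protected anyway. Serious AEs are collected to the follow-up visit, and related ones learned of later must be reported (8.3.1). Serious AEs and AEs of special interest are followed to resolution or stabilization (8.3). Clinically significant laboratory values are repeated (8.2.5). This stands too. What remains exposed is new non-serious AEs and neutropenia first arising after the ETV.

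On prohibited therapy, a reader might infer from the permission for other therapy in Period 4 that a participant could start a prohibited agent and simply stay in the treatment periods. The text does not support that: the permission applies only once Period 4 has begun, and the two rules can be read in sequence (stop, ETV, Period 4, new agent). The permission shows only that a new agent is compatible with follow-up.

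**Conclusion.** The contradiction is real but minor. The closing sentence of the ETV paragraph in 7.2 conflicts with 4.1 and 4.1.4, and no text exempts exits under 7.2 or limits the sentence to withdrawal of consent. If followed literally, it costs each affected participant Visit 801 with its neutrophil count and 24 to 32 days of collection of new non-serious AEs.

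Three stronger readings should be resisted. A reader might infer that the sponsor chose to forgo follow-up in these participants; the surrounding text points the other way. A reader might infer that the primary safety result is at risk; Section 9.5.5.1 counts events after the ETV as follow-up emergent and not as treatment-emergent, so the Week 0 to 24 summary is hardly affected. A reader might take 25 as the number who lose follow-up, or as an upper limit; it is a planning figure for discontinuation from all causes, and the documents give no basis for any share of it.

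The size per participant rests on the visit window alone. The shorter observation after the last dose rests also on the assumed ETV timing, and the 24 to 32 days would be gained only if the participant attends Visit 801.

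**What to change.** Reword 7.2 only. Limit immediate discontinuation from the study to withdrawal of consent and to cases where follow-up is not possible, such as loss to follow-up, entry into another incompatible study, or a regulatory or legal stop that rules it out. State that all other dosed participants, in particular those leaving by investigator discretion or for need of a prohibited therapy, stop study intervention, have the ETV (before the new agent where possible) and enter Period 4 under 4.1.4, with AE collection through Visit 801. In the prohibited-therapy item, replace discontinuation from the study with discontinuation from study intervention.

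The cost is a small text change and a few more Visit 801 attendances among participants who would otherwise have left at the ETV. The visit is already in the Schedule of Activities, so no new procedure is needed.

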7.2.1. Discontinuation of Inadvertently Enrolled Participants

If the Sponsor or investigator identifies a subject who did not meet enrollment criteria and was inadvertently enrolled, a discussion must occur between the Lilly clinical pharmacologist and the investigator to determine if the participant may continue in the study. If both agree that it is medically appropriate to continue, the investigator must obtain documented approval from the Sponsor to allow the inadvertently enrolled participant to continue in the study with or without continued treatment with ixekizumab. Safety follow-up should be performed as outlined in the SoA (Section 1.3), Safety Assessments (Section 8.2), and Adverse Events and Serious Adverse Events (Section 8.3) of the protocol.

7.3. Lost to Follow up

A participant will be considered lost to follow-up if he/she repeatedly fails to return for scheduled visits and is unable to be contacted by the study site. Site personnel or designee are

expected to make diligent attempts to contact participants who fail to return for a scheduled visit or were, otherwise, unable to be followed up by the site.

Site personnel, or an independent third party, will attempt to collect the vital status of the participant within legal and ethical boundaries for all participants enrolled, including those who did not get investigational product. Public sources may be searched for vital status information. If vital status is determined to be deceased, this will be documented, and the participant will not be considered lost to follow-up.

The Sponsor personnel will not be involved in any attempts to collect vital status information.

8. Study Assessments and Procedures

Study procedures and their timing are summarized in the SoA (Section 1.3).

Immediate safety concerns should be discussed with the Sponsor immediately upon occurrence or awareness to determine if the participant should continue or discontinue study intervention.

Adherence to the study design requirements, including those specified in the SoA, is essential and required for study conduct.

All screening evaluations must be completed and reviewed to confirm that potential participants meet all eligibility criteria. The investigator will maintain a screening log to record details of all participants screened and to confirm eligibility or record reasons for screening failure, as applicable.

The joint assessor (or designee) should be a rheumatologist, trained dermatologist or skilled joint assessor and will be responsible for completing the joint counts for swelling, tenderness, and limited range of motion. Additionally, the assessor will perform the following assessments: Physician's Global Assessment of Disease Activity, PASI, BSA.

To ensure consistent skin and/or joint evaluation throughout the study, individual participants should be evaluated by the same assessor for all study visits whenever possible.

Investigators or relevant clinical staff will provide age-appropriate explanations to all study participants prior to any assessment or procedure.

